7.1.2. Handling of Missing Data

No imputation of data will be carried out in case of missing data, but all available data will be used to its full extent.

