5.1.2. Intention to Treat Set or Full Analysis Set (FAS)

All randomized subjects who have taken at least one dose. These subjects will be assigned to the corresponding treatment group.

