7.1.7. Adjustments for Covariates

This study will use the draft guidance Adjusting for Covariates in Randomized Clinical Trials for Drugs and Biological Products - Guidance for Industry (CDER, May 2021, Revision 1). All baseline characteristics will be used to study exacerbations appearance in time using a Poisson regression or equivalent (see below).

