7.1.9. Model Assumptions

Primary endpoint analysis will use a median test or a Mann-Whitney test. Secondary endpoints will use relevant tests (Fisher's exact, T test, etc.) and a Poisson regression for exacerbations with baseline characteristics as covariates.

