7.4. Efficacy Evaluation

The efficacy analyses will be conducted based on all the analysis sets.

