7.4.1. Primary Efficacy Analysis

The rate of exacerbations per patient and the severity of these exacerbations will be compared using the chi-square test or Fisher's exact test. The relative risks will be estimated together with their 95% CI and median or Mann-Whitney tests. The number needed to treat (NNT) or number of events prevented per treatment will be estimated.

The rate of episodes occurred over time will be calculated, and the hazards ratio (HR) will be estimated together with its 95% CI following a Cox proportional-hazards model. The NNT (number of patients that need to be treated to avoid an event) will also be estimated.

Poisson model with robust estimation of incidence density will be used to include covariates in the model.

Poisson model assumes that the response variable is a count variable (number of exacerbations) and each subject has the same length of observation time. If the observation time for subjects varied, the Poisson model would need to be adjusted to account for the varying length of observation time per subject. In this case a Stata exposure option, *exposure(varname)*, will be used where *varname* corresponds to the length of time an individual was followed to adjust the Poisson regression estimates. Also, Poisson model assumes that the dependent variable is not over-dispersed and does not have an excessive number of zeros (in whose case Negative Binomial and Zero-inflated models would be preferred).

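### No imputation plus all baseline characteristics as covariates drops every FAS patient with one blank baseline value from the adjusted exacerbation model

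*SAP*

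**What the plan says.** SAP 7.1.2 sets one rule for every gap in the record: "No imputation of data will be carried out in case of missing data, but all available data will be used to its full extent". It does not separate baseline covariates from outcomes.

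SAP 7.1.7 sets the covariates: "All baseline characteristics will be used to study exacerbations appearance in time using a Poisson regression or equivalent". No list or count is given. SAP 7.4.1, under the primary efficacy heading, adds: "Poisson model with robust estimation of incidence density will be used to include covariates in the model". SAP 7.1.9 places what appears to be the same model among the secondary analyses, as "a Poisson regression for exacerbations with baseline characteristics as covariates", and says of the primary endpoint: "Primary endpoint analysis will use a median test or a Mann-Whitney test".

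SAP 7.4 states: "The efficacy analyses will be conducted based on all the analysis sets". The intention-to-treat set, or FAS, is defined in SAP 5.1.2 as "All randomized subjects who have taken at least one dose", so complete baseline data are not a condition of membership.

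Protocol 10.5 has a different missing-data rule: last observation carried forward (LOCF).

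**The concern.** A Poisson regression is fitted to patients with a value for every variable in it. With imputation ruled out and every baseline characteristic entered, one blank laboratory result or visual scale score excludes a patient whose exacerbations were fully recorded. The adjusted model is labelled as an FAS analysis but is fitted to whichever patients have complete covariates. That subset is not defined in advance, and its denominator differs from that of the unadjusted test reported beside it.

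This matters because, of the planned analyses of the exacerbation count, the Poisson model is the only one specified with an adjustment for length of follow-up (SAP 7.4.1). The sample-size section expects 20-25% dropout, so follow-up will vary. The SAP is also unclear whether the model is primary or secondary, so it may carry more weight than a supporting analysis.

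**Working it through.** **Does the rule lead to exclusion?** Four SAP statements combine: no imputation (7.1.2), all baseline characteristics as covariates (7.1.7, 7.4.1), efficacy analysed on every set (7.4), and an FAS that needs only randomisation and one dose (5.1.2). The promise in 7.1.2 to use all available data names no method that would keep a patient with a blank covariate in a regression. LOCF in Protocol 10.5 does not help either, because a baseline laboratory or spirometry value has no earlier trial measurement to carry forward. Followed as written, the plan drops the patient.

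**Inputs for the size.** The plan gives no figure on this point, so there is none to reproduce.

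- N = 180, the planned total (SAP 7.1.1), used only as a denominator. Nothing here depends on how it was derived.
- k, the number of covariates: not stated. Assumed 10 to 20. The baseline column of Table 1 has about 15 rows that yield data, and several (haematology, chemistry, spirometry, immunology) hold more than one variable.
- m, the fraction missing per covariate: not stated. Assumed 1% to 2%.

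**Independent missingness.** Loss L = 1 − (1 − m)^k. With the same information per remaining patient, the confidence interval widens by the factor 1/√(1 − L).

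| k | m | L | Lost of 180 | CI width factor |
|---|---|---|---|---|
| 10 | 1% | 1 − 0.99^10 = 9.6% | 17 | 1.05 |
| 15 | 1% | 1 − 0.99^15 = 14.0% | 25 | 1.08 |
| 15 | 2% | 1 − 0.98^15 = 26.1% | 47 | 1.16 |
| 20 | 2% | 1 − 0.98^20 = 33.2% | 60 | 1.22 |

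Outside these assumptions the range is wide: k = 5 with m = 0.5% gives 2.5%, and k = 20 with m = 5% gives 64%.

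**Clustered missingness.** A missed blood draw loses several variables at once. Let each covariate be missing when a latent normal variable exceeds its 1 − m quantile, with a common correlation ρ between covariates. Then L = 1 − E[Φ((z − √ρ·X)/√(1 − ρ))^k], where z is the 1 − m normal quantile and X is standard normal.

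| ρ | k = 10, m = 1% | k = 20, m = 2% |
|---|---|---|
| 0 | 9.6% (17) | 33.2% (60) |
| 0.5 | 6.7% (12) | 17.9% (32) |
| 0.9 | 2.9% (5) | 6.4% (12) |
| same patients miss everything | 1% (2) | 2% (4) |

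The figures in brackets are patients lost of 180.

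**After a change.** Filling missing baseline covariates brings the loss from this cause to 0. Cutting the list to three covariates without filling leaves 1 − 0.99^3 = 3.0% to 1 − 0.98^3 = 5.9%, or about 5 to 11 of 180.

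**The case against.** The best case for the plan is that the loss may be small. FEV1, pack-years and age are tied to eligibility, and immunoglobulins are drawn to rule out immunodeficiency, so these should rarely be blank in a randomised patient. Smoking, exhaled CO, both visual scales and the CAT are scheduled at the baseline visit and again at Visit 1. Every CRF is to be monitored to prevent data loss (Protocol 10.5), and omissions must be justified (Protocol 14). SAP 7.1.7 also allows an equivalent to Poisson regression, and nothing says that every laboratory value enters one model. All of this stands as a reason not to fix on a large figure. It does not remove the exclusion, because no section says what happens to a patient with a blank covariate, and the unlisted set of covariates does nothing to limit the loss.

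A reader might infer three stronger things that the documents do not support.

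- That the treatment effect will be biased. Characteristics recorded before randomisation are missing independently of the assigned arm, so the complete cases remain a randomised comparison. The demonstrable harm is lost precision and a shifting denominator.
- That the primary endpoint test is compromised. The median or Mann-Whitney test uses no covariates.
- That SAP 7.1.2 contradicts itself by promising to use all available data. That wording can fairly be read as an available-case rule, under which each patient contributes to whichever analyses their data permit.

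**Conclusion.** The point holds for the covariate-adjusted exacerbation model only. Following the SAP as written removes any FAS patient with one missing baseline covariate, so the model is fitted to an unplanned subset with wider intervals.

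The size cannot be taken from the documents. About 10% to 33% (17 to 60 of 180, interval about 5% to 22% wider) rests on three assumptions: 10 to 20 covariates, 1% to 2% missing on each, and independence. A reader might take that range as an expected loss, but it is an illustration. With clustering the same two corner cases give about 3% to 18%, and 1% to 2% if the same patients miss everything. The plan should be changed because the remedy is cheap and the loss is avoidable, whatever its true size.

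**What to change.** In SAP 7.1.2, exempt baseline covariates from the no-imputation rule. Fill a missing baseline value by single imputation from the pooled baseline data (the overall mean, or a missing category for categorical variables), without using treatment arm or outcome. Every FAS patient with outcome data then stays in the model.

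Preferably also replace all baseline characteristics in SAP 7.1.7 with a short named list. Report the number of patients analysed beside each model.

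Two related conflicts need separate reconciliation: the missing-data rule for outcomes (LOCF in Protocol 10.5, no imputation in SAP 7.1.2), and whether the Poisson model is primary (SAP 7.4.1) or secondary (SAP 7.1.9).

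The cost is a sentence or two in the SAP and a few lines of code. The downside is slight attenuation of the imputed covariate's own coefficient, which is not the quantity of interest.

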7.1.3. Blinding

This is a prospective, multicenter, randomized, double-blind clinical trial comparing a treatment group with a placebo group. The ratio between the group receiving active treatment (group I) and the group receiving placebo (group II) is 1:1.

7.1.4. Randomization

Randomization will be done in blocks of 6, using a list of random numbers (randomization list) generated by the Head of the Clinical Epidemiology and Clinical Research Methodology Unit of Health Research Institute Hospital Universitario Clínico San Carlos, Madrid, Spain. A Stata user program was used to produce the randomization list.

The treatment assignment should always be carried out starting with the lowest number and progressing in a correlative way in increasing order.

7.1.5. Multiple Comparison

If multiple comparisons are needed, Holm adjustment for multiple comparisons will be used. However, the analysis will try to obviate multiple comparisons except as exploratory analysis.

7.1.6. Interim Analysis

There is no interim analysis planned.

7.1.7. Adjustments for Covariates

This study will use the draft guidance Adjusting for Covariates in Randomized Clinical Trials for Drugs and Biological Products - Guidance for Industry (CDER, May 2021, Revision 1). All baseline characteristics will be used to study exacerbations appearance in time using a Poisson regression or equivalent (see below).

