5.1.3. Per Protocol Analysis Set (PP)

Randomized subjects completing the 50-week efficacy assessment period and adequately complying with the protocol. These subjects will be assigned to the actual treatment group. Any significant deviation from the treatment schedule will result in an exclusion from the "per-protocol" dataset.

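### SAP 7.1.7 enters every baseline characteristic, unlisted, into a robust-variance Poisson model with no small-sample correction: the adjusted 95% interval falls about 1–2 points short if ten terms are used, and further with thirty

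*SAP*

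**What the plan says.** SAP 7.1.7 sets the covariate rule: "All baseline characteristics will be used to study exacerbations appearance in time using a Poisson regression or equivalent (see below". SAP 7.1.9 repeats it among the secondary methods as "a Poisson regression for exacerbations with baseline characteristics as covariates". SAP 7.4.1, under the primary efficacy analysis, adds: "Poisson model with robust estimation of incidence density will be used to include covariates in the model".

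No section says which characteristics are meant, how many there are, or how they are coded. SAP 7.3 covers only their descriptive summary and names none. The baseline column of Table 1 holds about fifteen kinds of assessment that could supply a covariate: demographics, vital signs, tobacco use, history and examination, exhaled CO, hematology, chemistry, serology, immunology, spirometry, concomitant medication, resource use, two visual analog scales and quality of life. Several of these contain many variables.

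Protocol 10.1 has a different rule: look for confounding first, and adjust only for what is found.

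The full analysis set is "All randomized subjects who have taken at least one dose". For unequal follow-up, 7.4.1 says "the Poisson model would need to be adjusted to account for the varying length of observation time per subject", through an exposure term. For overdispersion or excess zeros it names other models, "in whose case Negative Binomial and Zero-inflated models would be preferred". On the primary test, 7.1.9 says: "Primary endpoint analysis will use a median test or a Mann-Whitney test".

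**The concern.** A robust (sandwich) variance is built from squared residuals. Each extra term lets the model fit the data more closely and shrinks those residuals, so without a correction the standard error is too small and the interval too narrow. The effect is small when terms are few relative to subjects. Here the number of terms is open and only 180 subjects are planned.

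Two things are at stake. First, the adjusted rate ratio could carry an interval that is not a true 95% interval. Second, the adjusted result is not fixed in advance: two analysts could follow the SAP, or the SAP and protocol 10.1, and report different adjusted estimates. Adding non-prognostic terms also gives back some of the precision that adjustment is meant to bring.

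**Working it through.** The plan gives no coverage figure to reproduce. The only benchmark is the nominal 95%.

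**Inputs from the documents.** 180 subjects, 1:1 (SAP 7.1.1). Dropout 20–25%, midpoint 22.5%. Placebo decrease 30%. Entry criterion of three moderate exacerbations in the prior year, giving an assumed placebo rate of 3 × (1 − 0.30) = 2.1 per year.

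**Assumptions.** The number of terms, the dispersion, the strength of prognostic covariates, and follow-up for dropouts uniform over 0.05–1 year. Covariates alternate between normal and binary (30%). Scenario A: dispersion 0.5. Scenario B: dispersion 0.4, with three prognostic covariates at 0.25 log-rate per SD. Scenario F: dispersion 1.0. (Scenarios C–E, mentioned below, change the rate to 1.5 or 3.0, or the dispersion to 0.3.)

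**Method.** Log-link Poisson with log follow-up time as offset, and no treatment effect. Variance = A⁻¹BA⁻¹, where A = Σ μᵢxᵢxᵢ′ and B = Σ (yᵢ − μᵢ)²xᵢxᵢ′, times n/(n−1). Interval = estimate ± 1.96 SE.

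**Hand check.** With q parameters (covariate terms plus intercept and treatment), the SE shrinks by roughly √((n − q)/n).
- 4 terms: √(174/180) = 0.983; 1.96 × 0.983 = 1.927; two-sided tail 5.4%.
- 10 terms: √(168/180) = 0.966; 1.893; tail 5.8%.
- 30 terms: √(148/180) = 0.907; 1.777; tail 7.6%.

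This omits uneven leverage and the noise in the variance estimate, so the true figures should be somewhat higher.

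**Simulation.** Non-coverage in %, n = 180, 6,000 trials per cell (Monte Carlo SE 0.3–0.4 points):

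| Covariate terms | A | B | F |
|---|---|---|---|
| 0 | 5.2 | 5.4 | 5.6 |
| 4 | 5.6 | 5.8 | 6.1 |
| 10 | 6.5 | 7.2 | 6.9 |
| 30 | 8.8 | 9.9 | 9.5 |

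A separate run of the same design with 12,000 trials per cell gave 6.4, 6.9 and 6.5% with ten terms. Its no-covariate cells were 5.2, 6.1 and 5.4%. A differently built run, with no dropout and rates of 2.1 against 1.2 (an actual effect), gave coverage of 93.4–94.0% with ten terms and 91.0–91.9% with thirty.

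**Negative binomial alternative**, scenarios A–F, 5,000 trials per cell: non-coverage 5.9–7.1% with ten terms and 7.9–9.3% with thirty. Switching model does not remove the problem. Zero-inflated models were not tested.

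**Per-protocol set.** SAP 5.1.3 limits this to "Randomized subjects completing the 50-week efficacy assessment period and adequately complying with the protocol". With 180 × 0.775 ≈ 140 subjects, robust Poisson non-coverage is 6.5–7.1% with ten terms and 9.4–10.8% with thirty (scenarios A and B).

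**Precision**, scenario B, true SD of the log rate ratio: 0.171 unadjusted, 0.155 with four terms, 0.163 with ten, 0.170 with thirty. As variance ratios to no adjustment: (0.155/0.171)² = 0.82, (0.163/0.171)² = 0.91, (0.170/0.171)² = 0.99.

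**Corrections.** HC2 divides each squared residual by (1 − leverage). With a t reference on n − q degrees of freedom, it brings the ten- and thirty-term cells of the table back to 5.1–5.9%. Scaling the sandwich by n/(n − q) with the same t reference leaves up to about 6.6–7%.

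**The case against.** The strongest reply is that the effect is small and its reach limited. Most of this is fair.

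- **Size.** With ten terms the gap is one to two points, and part of it is there with no covariates. Cutting ten terms to four recovers 0.9, 1.4 and 0.8 points in the table, or about one point.
- **Term count.** The documents state neither ten nor thirty. A reader might infer from Table 1 that the plan commits to thirty or more terms. It does not: the baseline column shows only that a literal reading could go that far.
- **Primary result.** A reader might infer that the trial's primary test is compromised. The documents do not support that, because 7.1.9 names an unadjusted median or Mann-Whitney test. Section 7.4.1 does place the Poisson model under the primary analysis, so its role needs stating, but that is a separate inconsistency.
- **Precision.** Ten terms still beat no adjustment when some are prognostic. The gain is gone only by about thirty.
- **A 92% worst case.** One ten-term cell of 5,000 trials in scenario B gave 7.8% non-coverage. Repeat runs gave 7.2% and 6.9%, so it should not be quoted as a worst case.
- **The interval is inferred.** The Poisson sentences in 7.4.1 do not themselves state a 95% interval. The relative risk and hazard ratio there do carry one, so the same is presumed here.
- **Software defaults.** SAPs often leave the finite-sample factor to the software. That is reasonable for a short list, but not when every baseline variable is to enter. The guidance cited in 7.1.7 is not available here and cannot be credited with a list.

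What stands is an open covariate rule, a conflicting rule in the protocol, and an interval that narrows too far as the rule is taken more literally.

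**Conclusion.** The point holds as a moderate one about the adjusted rate ratio only. At 180 subjects its nominal 95% interval covers about 93–94% if ten terms are used and about 90–92% if thirty are used, against about 94–95% with zero to four. Up to about half a point of the shortfall is present without covariates, slightly more in some cells. These figures rest on assumed event rates, dispersion and covariate strength, and the number of terms is itself an assumption.

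Adjustment is not the fault; a short list of prognostic covariates improves precision. The fault is the unbounded rule combined with an uncorrected robust variance. It is worth correcting before unblinding because the remedy is only wording and also settles the conflict with protocol 10.1.

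**What to change.** Before unblinding:

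1. Replace the covariate sentence in SAP 7.1.7 with a short fixed list of prognostic covariates and their coding. An example is FEV1 % predicted, smoking, age, and the prior-year exacerbation count if the CRF records it. Use the same list in 7.1.9 and 7.4.1, and state there whether the adjusted model is primary or secondary.
2. State in the SAP that this list supersedes the confounding-triggered rule of protocol 10.1. If it is too late for an amendment, record it as a deviation from the protocol.
3. If about ten or more terms are kept, specify an HC2-type variance with a t reference. This is preferable to residual-degrees-of-freedom scaling, which leaves up to about 6.6–7% non-coverage.

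Other baseline variables stay descriptive under 7.3.

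Cost: edits to three SAP sections, one statement about the protocol, and a check of the CRF for the prior-year count. FEV1, smoking and age are already needed for eligibility. The downside is that minor covariates are no longer adjusted for.

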7.1.8. Multicenter Trials

Statistical analysis will pool all available data from participating centers. There is no intention to compare centers in relation to the objectives of the study.

7.1.9. Model Assumptions

Primary endpoint analysis will use a median test or a Mann-Whitney test. Secondary endpoints will use relevant tests (Fisher's exact, T test, etc.) and a Poisson regression for exacerbations with baseline characteristics as covariates.

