6.1.1. Primary outcome

The primary efficacy outcome is a decrease in the mean number of COPD exacerbations. A clinical diagnosis of an exacerbation according to the GOLD definition will be considered; that is, an event occurring throughout the natural course of the disease, characterized by a change of acute onset, beyond the daily variability, in the patient's dyspnea, cough, and/or expectoration, which may require a change in the patient's usual medication.

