7.1.1. Sample Size and Power

The calculation of the sample size is based on the efficacy measured based on the decrease in the number of episodes of COPD exacerbations during the 12-month treatment period of the trial per subject.

The ratio of subjects to be distributed among the active treatment and placebo groups will be 1:1.

We estimate that subjects from group I (active treatment with the bacterial vaccine) will achieve a 60% decrease in their number of COPD exacerbations compared with a 30% decrease among those of group II (placebo). With an alpha error of 0.05 and a beta error of 0.2, and assuming a dropout rate of 20-25%, the number of subjects to be recruited would be 90 per study group, with an overall total of 180 trial subjects.

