7.4.2. Secondary Efficacy Analysis

The following variables will be analyzed to determine whether they follow a normal distribution: number of exacerbations, duration of the episodes, need for antibiotic therapy, number of hospital admissions, duration of the hospital admissions, immunological outcomes described in the trial design, quality of life, and direct costs.

These variables will be described together with their mean and standard deviation, or, in case of asymmetry, with their median and interquartile range. Differences between the means will be analyzed using Student's T test in the case of variables with a normal distribution and Mood's median test in the case of variables without a normal distribution. The absolute effect (difference in estimators) and its precision will be estimated with a 95% confidence interval (CI) in all cases.

The appearance of the first exacerbation will be studied at 3, 6, 12 months and whole study in the intention to treat (ITT) and per protocol (PP) sets and these same limits will be studied in the moderate and severe COPD populations. The appearance of any exacerbation at 3, 6, 12 months and whole study will be studied in the ITT and PP sets.

Number of exacerbations will be studied in the mild, moderate and severe COPD populations at 3, 6, 12 months and whole study. Number of exacerbations in the ITT and PP sets will be studied at 3, 6, and 12 months.

To compare the change in the immunological variables described in the trial design at 0, 3, 6, 12, and 18 months, an analysis of covariance will be performed, estimating the mean difference over time in both study groups.

The cost-benefit ratios in the study groups will be estimated together with their 95% CI, and compared using non-parametric tests.

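### SAP 7.1.9 names a primary test that ignores follow-up time, SAP 7.4.1 lists time-adjusted models beside it, and nothing says which result decides

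*SAP*

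**What the plan says.** SAP 6.1.1 defines the endpoint: "The primary efficacy outcome is a decrease in the mean number of COPD exacerbations". No unit of time is attached. SAP 7.1.1 ties the sample size to the 12-month treatment period.

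Two SAP sections then describe the primary analysis differently.

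- **SAP 7.1.9** gives one sentence: "Primary endpoint analysis will use a median test or a Mann-Whitney test". The next sentence assigns to the secondary endpoints "a Poisson regression for exacerbations with baseline characteristics as covariates".
- **SAP 7.4.1** (Primary Efficacy Analysis) lists chi-square or Fisher tests, then "The relative risks will be estimated together with their 95% CI and median or Mann-Whitney tests", a Cox model, and a robust Poisson model introduced as the way to bring in covariates. On follow-up it says: "If the observation time for subjects varied, the Poisson model would need to be adjusted to account for the varying length of observation time", using Stata's exposure option. Negative binomial and zero-inflated models are held in reserve. No method is called decisive.

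Four other provisions determine how unequal the follow-up can be.

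- The SAP full analysis set (5.1.2) requires one dose only. Protocol 10.7 also requires the week 25 assessment.
- SAP 7.1.2: "No imputation of data will be carried out in case of missing data, but all available data will be used to its full extent". Protocol 10.5 specifies last observation carried forward.
- Protocol 6.3.4 provides no follow-up of voluntary dropouts.
- The sample size is set "assuming a dropout rate of 20-25" per cent.

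**The concern.** A count of exacerbations means little without the time over which it was collected. A subject who leaves after one month with none gets the same rank as one who completes a year with none. In a median test both fall on the favourable side. With a fifth to a quarter of subjects expected to leave early, this affects a material share of the data.

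Two things are at stake. If dropout is equal between arms, partial-year counts blur the contrast and power falls. If dropout differs, the arm that loses more patients looks better, so the error can run in either direction. A rank or median test also does not test the mean number that SAP 6.1.1 names.

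Because 7.1.9 and 7.4.1 disagree on whether the Poisson model is primary, the analyst could obtain several results from one data set with no rule for choosing among them.

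**Working it through.** **The plan's own figure.** The only stated figure is 90 per group. Reading 60% versus 30% as two proportions, two-sided 5%, 80% power:

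n = [1.96·√(2·0.45·0.55) + 0.842·√(0.6·0.4 + 0.3·0.7)]² / 0.30² ≈ 42 per arm

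Allowing for dropout gives 42/0.80 = 53 to 42/0.75 = 56, so 90 is not reproduced. That is a separate matter; 90 per arm is taken as given below.

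**Assumptions not in the documents.**
- Baseline 3 exacerbations per year, suggested by the inclusion criterion of at least three moderate episodes. The plan's 30% and 60% decreases then give 3 × 0.7 = 2.1 (placebo) and 3 × 0.4 = 1.2 (active) per year.
- Between-patient (gamma) variance of the rate 0.3, 0.5 or 1.0.
- Leaving unrelated to the subject's own rate, with the splits and timings shown.

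**Why an early leaver ranks well.** For a Poisson count at 2.1 per year, P(no event) = exp(−2.1/12) = 0.84 over one month and exp(−2.1) = 0.12 over twelve. Most month-1 leavers score 0, tied for the lowest rank.

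**Size of the distortion in the raw count with no treatment effect.** The expected ratio of mean counts equals the ratio of mean time observed. With leaving uniform over the year, a leaver contributes half a year on average:
- 22.5% in both arms: ratio 1.
- 20% placebo, 25% active: (1 − 0.25·0.5)/(1 − 0.20·0.5) = 0.875/0.900 = 0.97.
- 15% placebo, 30% active: (1 − 0.30·0.5)/(1 − 0.15·0.5) = 0.850/0.925 = 0.92.

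**Type I error, two-sided 5%, 90 per arm, by simulation.**

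| Dropout, placebo vs active | Mann-Whitney on counts | Rate ratio with exposure |
|---|---|---|
| Equal 22.5% | about 5-6% | about 5-6% |
| 20% vs 25% | about 5% if uniform, 6-7% if early | 5-7% |
| 15% vs 30%, uniform | about 8-10% | 5-7% |
| 15% vs 30%, all before month 6 | about 12-17% | 5-7% |

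In the two 15% vs 30% rows the false positives almost all favour active.

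**Power at 2.1 vs 1.2 per year, equal 22.5% dropout, uniform leaving.**

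| Between-patient variance | 0.3 | 0.5 | 1.0 |
|---|---|---|---|
| Mann-Whitney | 89% | 83% | 63% |
| Rate ratio with exposure | 96% | 91% | 78% |
| Gap (points) | 7 | 8 | 15 |
| Gap with no dropout at all | about 3 | about 5 | about 10 |
| Remainder, due to ignored follow-up | about 4 | about 3 | about 5 |

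Mood's median test does worse: about 74% and 57% at variance 0.5 and 1.0.

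If the imbalance runs the other way (30% placebo, 15% active, uniform), Mann-Whitney power falls to about 75/63/46%, against 96/92/81% for the rate ratio.

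**The case against.** **Time-adjusted models are in the SAP.** A reader might infer that the SAP overlooks follow-up time in its primary analysis. It does not. The section headed as the primary analysis contains a Cox model, which can censor early leavers, and a Poisson model with exposure time. This stands, and it narrows the point to which result decides. It does not remove the point: 7.1.9 is the sentence that names the primary-endpoint test, and it names one without follow-up time. The exposure term is conditional on observation time varying, although dropout is already expected. The Cox model gives a hazard ratio, not a mean number of events.

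**Raw counts are an inference.** Section 7.1.9 does not name the variable tested, and 7.4.1 opens with a rate per patient. Ranking count divided by time gave type I error of about 5-7% even at 15% versus 30% dropout, although a zero after one month still ranks as a zero. The endpoint in 6.1.1 is a number, so the count reading is the natural one, but the text leaves it open.

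**Other provisions limit the exposure.** With protocol 10.7's week 25 condition, type I error was 4-6% even at 15% versus 30%. Protocol 6.3.3 replaces some subjects who leave before month 6. The per-protocol set contains only 50-week completers. All of this stands. However, the SAP set drops the week 25 condition, SAP 7.4 runs efficacy on every set without naming a primary one, and leavers between week 25 and month 12 remain under either definition.

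**First exacerbation.** The SAP says: "The appearance of the first exacerbation will be studied at 3, 6, 12 months and whole study". A reader might infer that early leavers will count as event-free in simple proportions. The text does not say so. Time to first exacerbation is a listed outcome and a Cox model is provided, so that reading is not supported.

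**Conclusion.** The point holds in a limited form and should be fixed. SAP 7.1.9 and 7.4.1 do not identify one decisive primary analysis. The test that 7.1.9 names, applied to the number of exacerbations in the one-dose set, takes no account of follow-up and does not test the mean that defines the endpoint.

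The dependable cost is power: about 7 to 15 points under equal dropout, of which roughly 3 to 5 come from ignored follow-up and the rest from the rank test itself. Mann-Whitney still reaches the planned 80% at variance 0.3 and 0.5, but not at 1.0.

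A reader might infer that the false-positive rate of this trial is materially inflated. The documents do not support that. They give 20-25% dropout overall and nothing by arm. At 20% versus 25% the error rate stays at about 5-7%. The 8-17% figures need an imbalance that is assumed here, and the upper part also needs all leaving to fall before month 6.

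The event rates, variances, dropout split and timing are all assumptions.

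**What to change.** State in both 7.1.9 and 7.4.1 that the primary analysis is the treatment rate ratio over months 0-12, with 95% CI, from the negative binomial or robust Poisson model already in 7.4.1. Choose one of the two in advance. Always include log of time observed within months 0-12 as an offset, not only if follow-up is found to vary. Run it on the SAP full analysis set and name that set as primary. Keep the Mann-Whitney test as a sensitivity analysis, stating whether it ranks counts or rates, and label the Cox and categorical analyses as supportive. Clarify the method for first exacerbation at 3, 6 and 12 months; Kaplan-Meier estimates would suit.

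The offset handles unequal time, not leaving that depends on a subject's own exacerbation rate, so a sensitivity analysis for informative dropout is also sensible.

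The cost is an SAP amendment before unblinding, with no new data: protocol 6.3.1 already records withdrawal dates. Protocol 10.1 prescribes a t test or Mood's median test for the number of exacerbations, so the change departs from it and must be described in the final report under protocol 10.6. The different ITT definitions (SAP 5.1.2, protocol 10.7) and missing-data rules (SAP 7.1.2, protocol 10.5) should be reconciled in the same amendment.
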